8.3. Analysis of secondary endpoints

8.3.1. Response

Due to practical considerations, our sample size will be limited to a maximum of 16 patients. CR rate will be reported as a proportion for the endpoint, along with the exact 90% confidence intervals for binomial proportion.

Prior reports indicate that the CR rate in this population of patients is around 30%.⁴⁹ In Table 7, we report the precision and compute the exact 90% confidence intervals for the CR rate assuming a range of reasonably anticipated values for the flotetuzumab treatment.

Table 7. CR rates and 90% exact binomial confidence intervals for maximum enrollment at a single dose level (N=10)

CR rate	20	30	40	50	60
Exact 90% CI	0-41	6-54	15-65	24-76	35-85

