2.6. Prognosis and Treatment of Post-Transplant Relapse in AML

When patients do relapse following alloHSCT, the prognosis is quite poor, but the non-tolerized allogeneic immune system may enhance the efficacy of treatment. A study of 263 AML patients who relapsed following a RIC alloHSCT demonstrated a subsequent CR rate of just 32% with a 2-year OS of 14% from the time of relapse.⁴⁹ Notably, 2-year OS after relapse was particularly poor among patients who were treated with chemotherapy alone (4.4-6.8%), whereas a purely immunologic strategy using donor lymphocyte infusion (DLI) resulted in an improved CR rate of 36% with a subsequently better 2-year OS of 25%, although some patients did go on to receive a second alloHSCT. In relapsed FLT3-mutated AML, deeper and more durable responses have been achieved with TKIs in the post-transplant setting than in patients who have been treated with chemotherapy alone.⁵⁰ The improved outcomes in post-transplant patients suggest that the non-tolerized allogeneic immune system augments the benefits of post-transplant therapies

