8.2. Study Design

This study proposal will be a phase 1 trial of flotetuzumab in patients with relapsed/refractory AML following alloHSCT. The first part of the study will be a dose escalation following a 3+3 design for post-transplant flotetuzumab. The study will start with the recommended dose of flotetuzumab in relapsed/refractory ALL (DL1). The first three patients will be enrolled and monitored for the first cycle of treatment for DLTs through the full DLT period (90 days) before enrolling additional patients. If less than 2 patients experience a DLT, an additional 3 patients will be enrolled. If 0 or 1 out of 6 patients have a DLT, then the dose will be deemed safe and considered the MTD of flotetuzumab in the post-transplant setting. If 2 or more of the first 3 or 6 patients experience a DLT, then the trial will proceed to enroll patients at DL-1 starting with 3 patients. The first three patients on DL-1 will be enrolled and monitored in the first cycle of treatment for DLTs through the full DLT period (90 days) before enrolling additional patients. If less than 2 patients experience a DLT at DL-1, an additional 3 patients will be enrolled at DL-1. If 0 or 1 out of 6 patients have a DLT at DL-1, then the dose will be deemed safe and the MTD. If 2 or more of the first 3 or 6 patients experience a DLT, then the trial will be stopped. An expansion cohort of 4 subjects will be also pursued at MTD for flotetuzumab to further characterize safety, tolerability and any preliminary signs of biological or clinical activity in this cohort. DLT monitoring will continue in this expansion cohort, and the trial will be stopped if two additional subjects experience a DLT. Any patient who discontinues treatment prior to the completion of one cycle of flotetuzumab for disease progression or for an adverse event that is not possibly, probably, or definitely due to the study treatment will be replaced.

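### Table 7 is labelled exact binomial, but its 90% intervals for the CR rate are normal-approximation (Wald) limits, and all five are narrower than the Clopper-Pearson intervals

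*Combined protocol and SAP*

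**What the plan says.** Section 8.3.1 (Response) commits the final analysis to exact intervals: "CR rate will be reported as a proportion for the endpoint, along with the exact 90% confidence intervals for binomial proportion". It then introduces Table 7 as a set of exact 90% intervals, computed "assuming a range of reasonably anticipated values for the flotetuzumab treatment". The table title repeats the claim, "Table 7. CR rates and 90% exact binomial confidence intervals for maximum enrollment at a single dose level (N=10"), and so does the row label. The row reads:

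| CR rate (%) | 20 | 30 | 40 | 50 | 60 |
|---|---|---|---|---|---|
| Printed 90% interval (%) | 0-41 | 6-54 | 15-65 | 24-76 | 35-85 |

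The denominator is consistent with Section 8.2. A dose is accepted on six patients ("If 0 or 1 out of 6 patients have a DLT, then the dose will be deemed safe"), and then "An expansion cohort of 4 subjects will be also pursued at MTD for flotetuzumab", so 6 + 4 = 10.

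Two other statements bear on how the table is read. On the historical rate, Section 8.3.1 says "Prior reports indicate that the CR rate in this population of patients is around 30"%. On total enrolment it says "Due to practical considerations, our sample size will be limited to a maximum of 16 patients".

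**The concern.** The 20% column shows the problem without any calculation. It corresponds to 2 responders out of 10, and its lower limit is printed as 0. Once a response has been seen, a true rate of zero is impossible, so no exact interval can start at 0. A zero there is what remains when a negative normal-approximation limit is truncated. The printed intervals are also symmetric about the point estimate, apart from that truncation, whereas exact binomial intervals away from 50% are not.

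At stake is the stated precision of the trial's only response endpoint. If the row is not exact, whoever runs the analysis as specified will obtain intervals that differ from the protocol's own table, and readers of the plan will have been shown more precision than the chosen method gives at ten patients.

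**Working it through.** **Inputs.** N = 10 and a two-sided 90% level (Table 7 title); CR rates of 20, 30, 40, 50 and 60% (Table 7), that is x = 2, 3, 4, 5 and 6 responders.

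**Step 1: reproduce the printed row.** The Wald limits are p ± 1.645·√(p(1−p)/10). For 20%, √(0.2·0.8/10) = 0.1265 and 1.645 × 0.1265 = 0.2081, giving −0.81% to 40.81%. For 60%, √(0.6·0.4/10) = 0.1549 and 1.645 × 0.1549 = 0.2548, giving 34.52% to 85.48%. The other columns follow in the same way.

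**Step 2: compute what the label promises.** The Clopper-Pearson 90% limits are the 5% quantile of Beta(x, 11−x) and the 95% quantile of Beta(x+1, 10−x).

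| x/10 | Printed | Wald | Clopper-Pearson | Printed width | Exact width | Shortfall |
|---|---|---|---|---|---|---|
| 2 | 0-41 | −0.81 to 40.81 | 3.68-50.69 | 41 | 47.0 | 6.0 |
| 3 | 6-54 | 6.16-53.84 | 8.73-60.66 | 48 | 51.9 | 3.9 |
| 4 | 15-65 | 14.52-65.48 | 15.00-69.65 | 50 | 54.6 | 4.6 |
| 5 | 24-76 | 23.99-76.01 | 22.24-77.76 | 52 | 55.5 | 3.5 |
| 6 | 35-85 | 34.52-85.48 | 30.35-85.00 | 50 | 54.6 | 4.6 |

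Wald reproduces all ten printed limits. Clopper-Pearson agrees with only two after rounding (the lower limit at 40% and the upper limit at 60%).

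**Step 3: rule out other methods.** At 90% and N = 10, for x = 2 to 6:

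- Mid-P: 5-47, 11-57, 17-66, 25-75, 34-83.
- Wilson: 7-46, 13-56, 19-65, 27-73, 35-81.
- Agresti-Coull: 6-47, 12-56, 19-65, 27-73, 35-81.
- Jeffreys: 6-45, 12-56, 19-65, 26-74, 35-81.
- Blaker (another exact method): 5.5-50.0, 11.6-60.6, 18.8-65.9, 23.9-76.1, 34.1-81.2.

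None gives the printed row. Nor does Clopper-Pearson at 80% or 95%, or at 90% with N from 11 to 16.

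**Step 4: size of the error in probability terms.** At a correct exact limit the tail probability is 5%. At the printed limits it is:

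- P(X ≤ 2 | p = 0.41) = 15.2% (upper limit, 20% column).
- P(X ≥ 6 | p = 0.35) = 9.5% (lower limit, 60% column).

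**Step 5: coverage at N = 10, nominal 90%.**

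| True rate | 0.2 | 0.3 | 0.4 | 0.5 | 0.6 |
|---|---|---|---|---|---|
| Wald | 86.0% | 80.3% | 89.9% | 89.1% | 89.9% |
| Clopper-Pearson | 96.7% | 92.4% | 94.1% | 97.9% | 94.1% |

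**Step 6: the historical rate, as illustration.** With 6/10 responders the printed lower limit of 35% clears the 30% figure comfortably. The exact limit of 30.35% only just does, with P(X ≥ 6 | 0.30) = 4.7%. Section 2.6, with the same citation, reports that the source study "demonstrated a subsequent CR rate of just 32"%. The exact interval does not exclude that value, since P(X ≥ 6 | 0.32) = 6.4%.

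**The case against.** No reading rescues the row as exact, so the case on the other side concerns how much the error matters.

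- **Narrowness depends on the comparator.** Against Blaker's exact method the printed 40% and 60% columns are slightly too wide (50 points against about 47), and the 50% column matches. This stands. The shortfall of 3.5 to 6.0 points is relative to Clopper-Pearson, which is what exact binomial conventionally means.
- **The error is not uniform narrowing.** At 20% and 30% the printed lower limits sit below the exact ones (0 against 4, 6 against 9), while the upper limits fall about 10 and 7 points short. Those intervals are shifted down as well as shortened. This also stands.
- **Under-coverage is confined to the low rates.** Wald coverage is close to nominal at 40% to 60%, where Clopper-Pearson over-covers. In those columns the fault is mainly the label.
- **The plan tests nothing against 30%.** This is correct. At 6/10 the conclusion against 30% is unchanged, and it changes only against the 32% background figure. The endpoint in Section 8.1.2.1 is CR + CRi, and the documents do not say whether the 32% includes CRi, so the comparison may not be like for like. It serves only as illustration.
- **Nothing depends on the table.** Sample size is practical, dose and stopping rules rest on DLTs, and the final analysis is already specified as exact. This limits the severity but does not make the row correct.

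**Conclusion.** The concern holds. Table 7 is labelled exact throughout but contains Wald limits, and eight of its ten entries differ from the Clopper-Pearson values. The total width is understated by 6.0, 3.9, 4.6, 3.5 and 4.6 points at 20% to 60%. The largest single discrepancy is 9.7 points, in the upper limit at 20% (50.69 − 41 = 9.69). The identification of the method rests only on N = 10 and the 90% level, both printed in the title. The size of the shortfall also assumes that exact means Clopper-Pearson. The error should be fixed because it misstates the plan's only precision figures for CR, but it affects no dosing decision, stopping rule or correctly executed final analysis.

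**What to change.** Replace the interval row of Table 7 with the Clopper-Pearson values:

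| CR rate (%) | 20 | 30 | 40 | 50 | 60 |
|---|---|---|---|---|---|
| Exact 90% CI (%) | 4-51 | 9-61 | 15-70 | 22-78 | 30-85 |

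Name Clopper-Pearson in Section 8.3.1 as the method for both the table and the final CR analysis. The word exact does not settle the interval by itself: at 6/10, Blaker's method gives 34-81 where Clopper-Pearson gives 30-85.

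The cost is one table row and one phrase. The stated precision becomes somewhat less favourable. Patient numbers, DLT rules and stopping rules do not change.

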8.3.2. Toxicity-related Endpoints

The cumulative incidence of acute (grade I-IV, grade III-IV) and chronic GVHD (overall, and by extent) will be estimated through competing-risk analysis, wherein death is a competing risk for GVHD.

9. Data Safety and Monitoring Plan

The study PI will be responsible for the conduction of the study, including the monitoring of the study's safety and oversight of the data collection. The PI will follow the Data Safety and Monitoring plan outlined in the Sidney Kimmel Comprehensive Cancer Center's DSMP Policy.

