1.2.2. Toxicity-related Objectives

- 2) Assess acute GVHD incidence
- 3) Determine chronic GVHD incidence
- 4) Measure non-relapse mortality

2. Background

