4.6. Study Parameters

The studies planned during patient evaluation and therapy are listed in Table 3. This represents the basic follow-up plan and will change based on patient condition. All attempts will be made to collect all correlative studies, however, due to laboratory constraints (weekends, holidays, laboratory emergencies or staffing difficulties) and patient constraints (related to intercurrent disease, transportation, or inadequate sample), some samples will not be collected or will not be suitable for evaluation. A patient will be considered suitable for evaluation independent of the availability of correlative study material. A variation of +/- 3 days for all study testing and visits is permitted.

Table 3: Study Calendar

Pre-Treatment		Cycle 1			Subsequent Cycles			End of Treatment	Post-Treatment Follow-up
Parameter	Pre-treatment	Day 1	Day 8, Day 15, Day 22	Day 28	Day 1	Day 8, Day 15, Day 22	Day 28		
Screening/Administrative									
Informed Consent	X								
Pre-Treatment		Cycle 1			Subsequent Cycles			End of Treatment	Post-Treatment Follow-up
Parameter	Pre-treatment	Day 1	Day 8, Day 15, Day 22	Day 28	Day 1	Day 8, Day 15, Day 22	Day 28		
Demography/Medical History	X								
Eligibility Criteria	X								
Study Drug Administration									
Flotetuzumab		X	X		X	X			
Safety Assessments									
Physical Examination	X	X			X			X	
ECOG Performance Status	X	X			X				
Vital Signs	X	X			X				
Weight ¹	X	X			X				
Height	X								
ECG	X								
Concomitant Medications	Continuous from the time of signing of ICF until at least 30 days after the last dose of flotetuzumab								
Adverse Events	Continuous from the time of signing of ICF until at least 30 days after the last dose of flotetuzumab								
Laboratory Assessments									
CBC with Differential	X	X	X	X	X	X	X	X	
PT, PTT	X	X			X				

CMP	X	X	X	X	X	X	X	X	
Magnesium	X	X			X				
Phosphate	X	X			X				
LDH	X								
HBV surface antigen and hepatitis C (antibodies)	X								
HIV Antibody	X								
Serum HCG or urine pregnancy test for applicable women only	X	X			X				
Pre-Treatment		Cycle 1			Subsequent Cycles			End of Treatment	Post-Treatment Follow-up
Parameter	Pre-treatment Within 14 days prior to Day 1	Day 1	Day 8, Day 15, Day 22	Day 28	Day 1	Day 8, Day 15, Day 22	Day 28		
Peripheral Blood and Bone Marrow studies for MRD	X			X			X		
Bone Marrow studies for chimerism	X			X			X		

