Peripheral Blood and Bone Marrow studies for immunologic correlates	X		X (Day 15 ONLY/P B ONLY)	X			X (Cycle 2 ONLY)		X (at 6 and 12 months post-transplant and relapse) ⁴
Peripheral Blood serum samples for Cytokine Measurement	X ⁵	X ⁵	X ⁵						
Disease Evaluations									
Bone Marrow aspirate/biopsy	X			X			X	X	

MRD Assessment via Peripheral Blood and Bone Marrow ²	X			X			X	X	
Survival, subsequent therapy, other malignancies ³									X
¹ Must be assessed prior to dosing on Day 1 of each specified cycle, in case of weight loss of >10% within a cycle, the dose of study drug must be recalculated.									
² See section 5.5. MRD assessment will be performed on bone marrow using MFC as previously described by Gerber et al., where any detectable disease will be considered positive. ^{35,54} Samples will be sent for standard-of-care MFC from the bone marrow aspirate, and if a bone marrow aspirate cannot be obtained, then samples will be sent from the peripheral blood for standard-of-care MFC.									
³ This data will be obtained through standard-of-care provider visits that occur following alloHSCT.									
⁴ The correlative samples will be collected at the time of the patient's standard of care bone marrow biopsies that are performed at 6 and 12 months after transplant. There is considerable variability in the time at which these are performed.									
⁵ Samples will be collected pre-dose and once per infusion bag change.									

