4.12. Duration of Follow-up

Patients will be followed for relapse and death for two years from the first day of the first cycle of treatment. Patients are routinely followed and monitored by JH physicians after alloHSCT or chemotherapy, and patients who complete the study and continue to receive their care at JH will have survival captured annually.

5. Disease Evaluations

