8.1.2.2. Toxicity-related Endpoints

- 2) Report the incidence of acute GVHD
- 3) Report the incidence of chronic GVHD
- 4) Report cumulative incidence of non-leukemia mortality

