9.2. Management of Safety Data

This Study has been designated as an interventional study. As such, all adverse events/product quality complaints for study drug (flotetuzumab) regardless of causality and special situations will be reported from the time a subject has signed an Informed Consent Form (ICF) until 30 days after the last dose of study drug excluding those from subjects not exposed to study drug.

Serious adverse events will be reported for 30 days after the last dose of study drug.

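### Cumulative incidence of GVHD is planned with death competing, but after treatment GVHD is collected only through adverse-event reporting (last dose + 30 days), while death is followed for two years

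*Combined protocol and SAP*

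**What the plan says.** **Endpoint.** Section 1.2.2 lists acute GVHD incidence as a secondary objective and adds "Determine chronic GVHD incidence". Section 8.1.2.2 repeats both as endpoints, the second as "Report the incidence of chronic GVHD". Section 8.3.2 says the cumulative incidence of acute GVHD (by grade) and chronic GVHD (overall and by extent) "will be estimated through competing-risk analysis, wherein death is a competing risk for GVHD". It gives no time origin, horizon or censoring rule.

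**Follow-up.** Section 4.12: "Patients will be followed for relapse and death for two years from the first day of the first cycle of treatment". In the study calendar (Section 4.6, Table 3) the clinical item in the post-treatment column is "Survival, subsequent therapy, other malignancies". Its footnote 3 reads "This data will be obtained through standard-of-care provider visits that occur following alloHSCT". The only other entries in that column are correlative samples. No row of Table 3, at any visit, is for GVHD.

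**Adverse events.** The AE row of Table 3 reads "Continuous from the time of signing of ICF until at least 30 days after the last dose of flotetuzumab". Section 9.2 requires AE reporting "until 30 days after the last dose of study drug excluding those from subjects not exposed to study drug" and gives serious events the same 30 days. Section 9.3 closes AE reporting earlier if a new systemic anticancer therapy begins, and lets the investigator extend it where long-term drug effects are suspected.

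**Other GVHD text.** GVHD arising during treatment is a DLT (Section 6.2.1), and definite GVHD stops treatment (Section 4.7.5). Appendix 12.1 gives staging criteria but no assessment schedule. Section 4.2 censors results at a second alloHSCT.

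**The concern.** A cumulative incidence estimate needs, for each patient, an onset date and grade or extent if GVHD occurs, and otherwise a known date to which GVHD was looked for. The plan supplies the competing event (death) for two years, but requires capture of the event of interest only until shortly after treatment ends. Chronic GVHD is the endpoint most exposed, because later onset falls mainly outside that window.

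At stake is what the reported chronic GVHD figure means. Two analysts could follow Section 8.3.2 and produce different numbers: one censoring at the end of AE capture, the other keeping patients at risk as GVHD-free until death or day 730. This is a descriptive secondary endpoint in at most 16 patients, so no decision rule depends on it. It is, however, the transplant-specific toxicity that the protocol chose to estimate.

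**Working it through.** The plan states no horizon, event count or precision for GVHD, so there is no figure to reproduce. The check compares the two observation windows.

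**Inputs**
- Cycle length: 28 days (Section 4.2, Table 1).
- Required AE capture: 30 days after last dose (Sections 9.2 and 9.3; a minimum in Table 3).
- Follow-up for death: two years from Cycle 1 Day 1 (Section 4.12), taken as 730 days.
- Number of cycles: Section 4.11 plans up to five induction and two consolidation cycles, but its item 10 ends treatment on completing either two consolidation or five induction cycles. Both 5 and 7 are shown; the two statements should be reconciled.

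**Step 1: end of required capture without delays.** End day = 28 × cycles + 30.

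| Cycles | End of capture | Share of 730 days | Gap to day 730 |
|---|---|---|---|
| 1 | 28 + 30 = day 58 | 8% | 672 |
| 2 | 56 + 30 = day 86 | 12% | 644 |
| 5 | 140 + 30 = day 170 | 23% | 560 |
| 7 | 196 + 30 = day 226 | 31% | 504 |

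New systemic anticancer therapy within the 30 days shortens each figure under Section 9.3.

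**Step 2: delays.** One 14-day delay before each later cycle adds 14 × (cycles − 1) days: day 100 for 2 cycles, 226 for 5 and 310 for 7. This is not a ceiling. Section 4.11 item 9 limits only consecutive delay from unresolved toxicity, and Section 4.7.4 allows holds within a cycle. If held days were made up, which the documents do not say, one 14-day hold in each of 7 cycles would add 98 days: 310 + 98 = day 408.

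**Step 3: provisions that reach past last dose + 30 days.**
- The 90-day DLT period (Section 8.2) can outlast AE capture after one or two cycles. The GVHD criterion in Section 6.2.1 is confined to the treatment period, so afterwards only Grade 3–5 events at least possibly related to drug would qualify. Day 90 is still 730 − 90 = 640 days short.
- The Section 9.3 extension is discretionary.
- Section 9.7.2 follows serious events that are already open; it does not look for new GVHD.

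None of these schedules GVHD ascertainment.

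**Step 4: effect on the estimate.**
- Censor at the end of GVHD observation: the estimator can be used over the observed period, but the curve is short and its end depends on when treatment stopped. Censoring may then be informative.
- Carry patients as GVHD-free to day 730: unrecorded GVHD counts as absence of GVHD, and incidence is biased low.

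Section 8.3.2 does not choose between them.

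**The case against.** The strongest reply has four parts.

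**Unequal follow-up is not itself an error.** A competing-risk analysis can censor each patient when GVHD observation ends. This stands. A reader might infer that the planned estimate is necessarily biased low, but no passage says unobserved patients will be carried as GVHD-free to day 730. The low bias is conditional on that choice.

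**GVHD is already watched closely.** During treatment this is true, through the DLT and discontinuation rules, so the plan does not ignore GVHD and the dose decision is not compromised. After treatment, the standard-of-care visits supply only the items named in Table 3. Discretionary recording of some late cases does not provide the systematic ascertainment that a cumulative incidence curve needs.

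**Longer collection could mislead.** Section 4.10 anticipates donor lymphocyte infusion (DLI) and other therapy after relapse or treatment failure, and Section 2.6 describes DLI and second transplants in this setting. GVHD after those would not be flotetuzumab toxicity, and closing AE capture at new therapy may be deliberate. This stands: longer collection needs a rule for later therapy, and the second-transplant rule in Section 4.2 must be carried into the analysis.

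**The stakes are modest.** This is a descriptive secondary endpoint in a small study. That limits the priority but leaves the gap between the endpoint and its data.

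**Conclusion.** The point holds as a mismatch between a planned analysis and the data scheduled to support it. Without delays, required capture ends at day 58 to 226 for 1 to 7 cycles, 8% to 31% of the two-year follow-up for death. Later-onset GVHD, mainly chronic, is recorded only at discretion. This rests on 28-day cycles, on 30 days as the required minimum, and on no earlier closure for new anticancer therapy.

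Three further inferences are not supported:
- That capture can never reach one year. Delays extend it and the documents set no firm maximum (Step 2).
- That day 86 is the usual end for non-responders. Section 4.11 item 11 stops patients without at least PR after two successive cycles, but progression or GVHD can stop treatment sooner, and no distribution of cycles is given.
- That a particular number of GVHD events will be missed. The documents give no GVHD rate.

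The missing time origin is a lesser matter. Section 4.4 mentions GVHD timing after transplant only to explain when treatment may start, and Section 4.12 supplies Cycle 1 Day 1 as the natural origin. The change should be made, but it does not bear on the MTD.

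**What to change.** **Preferred.** Add GVHD status, onset date and grade or extent (Appendix 12.1 criteria) to the post-treatment follow-up in Table 3 and to Section 4.12, abstracted from the visits that footnote 3 already uses. In Section 8.3.2 state:
- the origin (Cycle 1 Day 1, as in Section 4.12) and a fixed horizon within two years;
- censoring at the last GVHD assessment, and the existing censoring at second alloHSCT from Section 4.2;
- how GVHD after DLI or other subsequent anticancer therapy is handled, for example by censoring at its start or treating that start as a competing event. The subsequent-therapy data are already collected.

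**Alternative.** Limit the endpoint expressly to GVHD up to last dose plus 30 days, and describe it that way wherever it is listed and reported.

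Under either option, reconcile Sections 9.2 and 9.3 on whether AE capture stops at new anticancer therapy.

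**Cost.** The preferred option needs an added case-report-form item abstracted from existing visits, plus wording in Sections 4.12, 8.3.2 and 9.2/9.3 and in Table 3; it needs no new visits or procedures. Its weakness is that standard-of-care visit timing varies, and patients who leave the centre may have incomplete GVHD dates. The alternative needs only wording, but gives up later chronic GVHD.
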